- 2) the levels of cytokine after stimulation of PBMC with *B. pertussis* antigens and unrelated antigens.
- 3) the cytokine levels in nasopharyngeal aspirate.

To explore the frequency and magnitude of colonization and as well as antibody, B and T cell responses in a small group of healthy adult volunteers with high PRN antibody levels (only highest vaccine dose).

V. Selection of volunteers

V.1. INCLUSION CRITERIA

Subject will be included in the study if he/she meets all the following criteria:

1. Healthy male or female between 18 and 32 years of age, vaccinated or unvaccinated with acellular pertussis vaccine.
2. Female subject of child bearing potential must be willing to ensure to use one of the following methods of contraception from 2 weeks before vaccination till one month after vaccination to avoid pregnancy during the study:
 - Complete abstinence from penile-vaginal intercourse
 - Double barrier method (male condom/spermicide, male condom/diaphragm, diaphragm/spermicide)
 - Any intrauterine device (IUD) with published data showing that the expected failure rate is <1% per year
 - Approved hormonal contraception (except low-dose gestagen), which is not contraindicated to study vaccine administration
3. Informed consent form (ICF) signed by the subject.
4. Subject shall be able to attend all scheduled visits and to understand and comply with the study procedures.

V.2. EXCLUSION CRITERIA

If any of the following criteria are met, the subject must not be included in the study:

1. Individual with PT and /or PRN serum IgG antibodies ≥ 20 IU/ml. NOTE! One control group with PRN serum IgG antibodies ≥ 20 IU/ml and PT serum IgG antibodies <20 IU/ml will be included.
2. Vaccinated with the study vaccine in the Child Innovac study (EudraCT number 2010-019936-11).
3. Pregnant or lactating women. Pregnancy not planned and to be avoided during the study by use of effective contraceptive methods.
4. Blood pressure after resting $\geq 150/90$ mm Hg at screening.
5. Heart rate after resting ≥ 80 bpm at screening.
6. Respiratory rate after resting ≥ 20 /minute at screening.
7. Unwillingness to refrain from the use of nicotine products from screening through day 28.
8. Use of narcotic drugs and/or a history of drug/alcohol abuse within the past 2 years prior to screening.
9. The subject has donated blood or suffered from blood loss of at least 450 ml (1 unit of blood) within 60 days prior to screening or donated plasma within 14 days prior to screening.

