10. Receipt of immunoglobulin, blood derived products, systemic corticosteroids or other immunosuppressant drugs within 90 days prior to day 0.
11. Asthma or other chronic respiratory problems.
12. Use of corticosteroids in the respiratory tract (e.g. nasal steroids, inhaled steroids) 30 days prior to day 0.
13. Receipt of a vaccine within the last 30 days prior to day 0 or planned vaccination within the next 30 days after day 0.
14. Known hypersensitivity to any component of the study vaccine.

15. Current participation in any other clinical trial or participation (and during the whole study) in any clinical trial in the previous 3 months prior to day 0.
16. Inability to adhere to the protocol, including plans to move from the area.
17. Family history (first degree) of congenital or hereditary immunodeficiency.
18. Past or present infection with HIV, hepatitis B or C.
19. Chronic conditions requiring ongoing active medical interventions, such as diabetes mellitus or cardiovascular disease.
20. Any autoimmune or immunodeficiency disease/condition (inherited or iatrogenic).
21. Any medical condition which, in the opinion of the investigator, might interfere with the evaluation of the study objective or might affect the safety of the individual, e.g. evolving encephalopathy not attributable to another identifiable cause within 7 days of administration of a previous dose of any vaccine, hospitalization due to major depression or history of suicidal attempt. .
22. Abnormal laboratory values outside the limit of normal values for the screening laboratory with clinical significance at the discretion of the investigator.
23. Person in frequent contact with children less than 1 year of age (parent, childcare worker, nurse, etc) or residence in the same household as persons with known immunodeficiency including persons on immunosuppressive treatment.

V.3. TEMPORARY CONTRAINDICATIONS

Reschedule vaccination and visit 2 if

- Febrile illness and/or oral temperature $\geq 38.0^{\circ}\text{C}$ at the time of vaccination.
- Upper respiratory infection (URI), rhinitis and/or rhinoconjunctivitis.

VI. Study plan and design

VI.1. PLANNED STUDY CALENDAR

FVFS	August 2015
FVLS	February 2016
LVLS	September 2016
Antibody assays	August 2015 – October 2016
Exploratory laboratory assays	April 2016 – December 2016
Statistical analysis	October 2016 – December 2016

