Any administration of concomitant medications or non-study vaccines after the Visit 2 (Day 0) will be recorded in the Diary by the subject and will be reported in the CRF by the investigator or delegate according to the following rules:

For **medications**, the trade name, route, dose, start date, stop date and indication should be recorded in the CRF.

For **non-study vaccines**, the trade name, route, injection side and injection site (if applicable) and date of vaccination should be recorded in the CRF.

The principal investigator will decide whether the volunteer can continue in the study or not.

VII.3. NOT ALLOWED MEDICATIONS & VACCINES

Not allowed medications and vaccines during the first month after vaccination

The following therapies should be avoided during the first month after vaccination.

- Antibacterial agents with an effect on *B. pertussis*, notably macrolides, azitromycin, tetracyclines, trimetoprim-sulphamethoxazole, quinolones.
- Immunoglobulin, corticosteroids for systemic use or for use in the respiratory tract (e.g. nasal steroids, inhaled steroids), other immunosuppressive or immunostimulating agents.
- Topical nasal therapies.
- Pertussis vaccines. No other vaccine is known to cross-react with pertussis vaccines. Therefore the volunteer can continue in the study if other vaccines are given. Vaccines which can be anticipated, though only rarely, are tetanus vaccine in case of a wound, influenza vaccines in case of an outbreak of influenza, vaccines intended for travellers in case the volunteer will perform a visit in other countries with short notice. If a journey is known and vaccines are planned already at the screening visit, the volunteer will not be included in the study.

If it is necessary to give a medication or a vaccine, this shall for obvious reasons be permitted. All medications and vaccines will be documented in the CRF. The volunteer will be followed as pre-planned for adverse events. The immunological part of the study can also continue, but the results from the volunteer should be reported separately in the statistical analyses.

If the volunteer needs a medication or a vaccine more than one month after inclusion in the study this will be registered and the principal investigator will decide whether the volunteer can continue in the study or not. But as far as possible the subject must be followed as scheduled.

VIII. Withdrawals/study termination

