1.1.2. SECONDARY OBJECTIVES

To assess after vaccination by a single ascending dose of the genetically modified *B. pertussis* strain in healthy adult volunteers:

1. the safety and tolerability of the vaccine over 6 months (group 1-4) and then 12 months (group 1-3) post-vaccination
2. the frequency of colonization of the human respiratory tract by live attenuated *B. pertussis* strain and its magnitude (in terms of colony forming units) over 28-days post-vaccination.
3. the levels of serum IgG and IgA antibodies to 4 different *B. pertussis* antigens (*pertussis* toxin (PT), filamentous hemagglutinin (FHA), pertactin (PRN), and fimbriae 2/3) over 6 months (group 1-4) and then 12 months (group 1-3) after vaccination.

Exploratory objectives

To assess the B and T cell immune responses to 4 different *B. pertussis* antigens (*pertussis* toxin (PT), filamentous hemagglutinin (FHA), pertactin (PRN), and fimbriae 2/3) over -12 months after vaccination by :

- the levels of IgA in nasopharyngeal aspirate.
- the cytokine levels in nasopharyngeal aspirate.
- the levels of secreted cytokines as well as the number of pertussis-specific T- and memory B-cells after stimulation of PBMC with *B. pertussis* antigens and unrelated antigens.
-

To explore the frequency and magnitude of colonization and as well as antibody, B and T cell responses in a small group of healthy adult volunteers with high PRN antibody levels (only highest vaccine dose).

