2.1.3. OTHER SECONDARY ENDPOINT

1) Colonization of the BPZE1 strain in the nasopharyngeal mucosa:

Per dose, group and randomized allocation:

- Number and proportion of participants who have been colonized by the modified *B. pertussis* strain BPZE1 at each post-vaccination visit
- Number of visits during which bacteria are detected
- Magnitude of bacterial colonization (number of cfu) per post-vaccination visit
- Cough, spasmodic cough and any symptom from the respiratory tract will be described for colonized and not colonized participants

2) Immunogenicity:

Per dose, group, colonized/not colonized and randomized allocation:

- IgG and IgA antibodies against PT, FHA, PRN, and fimbriae 2/3 in serum at visits 2, 4, 6, 7, 8, 9 and 10
 - Geometric mean levels
 - Number and proportion of participants with positive responses, defined by at least 100% increase from pre- to post-vaccination, to at least 4 times MLD after vaccination

Samples will be tested blindly for *pertussis* specific antibodies in batch for each group. Antibody levels to PT, FHA, PRN, and fimbriae 2/3 will be expressed in IU/mL calibrated against reference antisera from the National Institute for Biological Standards and Controls.

- **Analysis strategy**

The immunogenicity criteria analysis will be performed on the mITT population and based on available data (without missing data handling) with the hypothesis of MCAR.

A robustness analysis will be performed and missing values will be imputed by the median of immunogenicity values in the placebo group.

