3.1.2. MAJOR PROTOCOL DEVIATIONS

The other following deviations are described per category:

- Randomized participants who did not receive the trial intervention
- Participants who received the wrong intervention or incorrect dose
- Participants who received a forbidden concomitant intervention. The following therapies should be avoided during the first month after vaccination:
 - Antibacterial agents effective against *B pertussis*.
 - Immunoglobulin, corticosteroids for systemic use or for use in the respiratory tract (e.g. nasal steroids, inhaled steroids), other immunosuppressive agents or immunostimulating agents.
 - *Pertussis* vaccines.
 - Topical nasal therapies.

If it is necessary to give a medication or a vaccine, this shall be permitted for obvious reasons be permitted. All medications and vaccines will be documented in the case report form (CRF). The volunteer will be followed as pre-planned for adverse events. The immunological part of the study can also continue, but the results from the volunteer should be reported separately in the statistical analyses.

Deviations per participant are described.

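### The rule that reports results separately after an outside pertussis vaccine stops at month 1, so post-booster titres at 6 and 12 months are counted as BPZE1 data

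*Combined protocol and SAP*

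**What the plan says.** **Entry.** Protocol V.2, criterion 13, excludes "Receipt of a vaccine within the last 30 days prior to day 0 or planned vaccination within the next 30 days after day 0". It treats all vaccines alike. Inclusion criterion 1 admits people "vaccinated or unvaccinated with acellular pertussis vaccine".

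**First month.** Protocol VII.3 and SAP 3.1.2 list pertussis vaccines under the statement "The following therapies should be avoided during the first month after vaccination". A vaccine that is needed is still permitted and the immunological follow-up may continue, but "the results from the volunteer should be reported separately in the statistical analyses".

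**After the first month.** VII.3 has a different rule: "If the volunteer needs a medication or a vaccine more than one month after inclusion in the study this will be registered". The principal investigator then decides on continuation, and "But as far as possible the subject must be followed as scheduled". Nothing is said about analysis. The synopsis gives the continuation decision to the investigator and the sponsor together; VII.3 names the investigator alone.

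**Endpoints.** SAP 1.1.2 follows serum antibody levels "over 6 months (group 1-4) and then 12 months (group 1-3) after vaccination". SAP 2.1.3 lists serum samples at Visits 2, 4, 6, 7, 8, 9 and 10. A responder is someone whose value at least doubles from before vaccination and reaches four times the minimum level of detection. The cause of the rise plays no part.

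**Analysis set.** SAP 2.1.3: "The immunogenicity criteria analysis will be performed on the mITT population and based on available data (without missing data handling".

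**The concern.** VII.3 itself singles out pertussis vaccine as the one that interferes: it lets volunteers given other vaccines continue because none is known to cross-react. Yet the analysis protection against a pertussis vaccine ends at one month, while the antibody endpoints run to 6 and 12 months.

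The Visit 9 and 10 figures show whether the BPZE1 response lasts. A booster in a vaccine arm can turn a non-responder into a responder, or hide waning in someone who did respond. In a placebo recipient it creates a false background response. SAP 2.2.2 plans no between-arm comparison, so the placebo arm would not correct the vaccine-arm figures. The tables by colonized and non-colonized status are also exposed: a boosted, never-colonized person would look like a response without colonization.

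**Working it through.** **Plan's own figures.** The plan gives no figure for outside pertussis vaccination. The nearest relevant one is the upper 95% limit of 26% for 0 events in 12 (protocol XV.1, SAP 1.3). Exact two-sided limit: 1 − 0.025^(1/12) = 26.5%, which agrees with the plan apart from rounding.

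**1. Which samples are exposed**

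| Serum sample | Timing | Covered by the first-month rule? |
|---|---|---|
| Visits 4, 6, 7 | Days 7, 14, 21 (±1) | Yes |
| Visit 8 | Day 28 (−1; +7) | Essentially; the window can end at Day 35 |
| Visit 9 | 6 ± 1 months | No, for vaccines given after month 1 |
| Visit 10 (SAP, Groups 1-3) | 12 months | No, for vaccines given after month 1 |

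At the SAP's 30.4375 days per month, and taking the first month as 30 days, the uncovered time is 182.6 − 30 = 153 days to month 6 (84%) and 365.25 − 30 = 335 days to month 12 (92%). That is calendar time. In samples, four of the five post-dose serum draws to month 6 are protected.

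**2. Effect on the responder proportion (n = 12 per active arm)**

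One boosted person who would otherwise be a non-responder: 1/12 = 8.3 percentage points. Starting from no responders, 0/12 (95% CI 0 to 26.5%) becomes 1/12 (0.2 to 38.5%). If that person was already a responder, the proportion does not move but the geometric mean still does.

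**3. Effect on the geometric mean**

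Multiplying one of n titres by f multiplies the geometric mean by f^(1/n). The fold rise f is an assumption.

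| f | n = 12 | n = 6 (Group 4) |
|---|---|---|
| 4 | 1.12 | 1.26 |
| 10 | 1.21 | 1.47 |
| 30 | 1.33 | 1.76 |

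**4. How likely is it?**

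Uptake is not in the documents. For an assumed annual uptake r, the chance per person between Day 30 and day T is p = 1 − (1 − r)^((T − 30)/365.25). The chance of at least one booster among the 36 vaccinees of Groups 1-3 is 1 − (1 − p)^36.

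| Assumed r | To month 6 | To month 12 |
|---|---|---|
| 0.5% | 7% | 15% |
| 1% | 14% | 28% |
| 2% | 26% | 49% |
| 5% | 54% | 82% |

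**5. Before dosing**

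The PT/PRN screen at Visit 1 may be 6 weeks (42 days) old, and criterion 13 reaches back 30 days. The gap is at most 42 − 30 = 12 days, Day −42 to Day −31. A pertussis vaccine given then, after the screen, meets no exclusion. It precedes the Day 0 (Visit 2) sample, which is the baseline under SAP 2.3.2, by at least 31 days.

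**The case against.** Several existing controls count against the concern.

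- VII.2 requires the trade name and date of any non-study vaccine in the CRF, so a booster should be identifiable.
- Continuation is decided case by case.
- The exclusion grounds in SAP 2.1 are not exhaustive, and the Executive Committee could act on others.
- VII.3 turns away volunteers whose travel vaccines are already planned at screening.
- In the earlier study (III.2) only culture-positive subjects showed antibody rises, from day 14 or 28. A first rise at Visit 9 in a never-colonized person would stand out.
- The endpoint is secondary and descriptive, and a shift from 0/12 to 1/12 is small against its confidence interval.

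These points make a booster visible and limit its importance. None takes the post-booster titre out of the main table. Anyone following SAP 2.1.3 as written would include it, and a decision taken after the data are seen is weaker than a rule. The travel sentence is tied to a known journey and does not clearly cover a routine booster.

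The protocol ends at 6 months and Visit 10 appears only in the SAP. Criterion 13 therefore cannot fairly be faulted for the 12-month sample, but the SAP that analyses it can be asked for a rule.

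A reader might also infer that the ageing antibody screen produces false responders. The documents do not support that. Change is measured from a fresh Day 0 sample, so a booster between Day −42 and Day −31 would mainly raise the baseline and make a doubling harder to reach.

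**Conclusion.** The gap is real and limited. No analysis rule covers a pertussis-containing vaccine given after month 1, so titres drawn after it at Visits 9 and 10 count as BPZE1 data. One otherwise non-responding person per arm of 12 adds 8.3 points to the responder proportion, and the geometric mean rises by 12% to 33% for an assumed 4- to 30-fold rise. These sizes assume that the vaccine raises the antibody concerned and, for the proportion, that the responder threshold is met. Frequency is unknown, so the documents do not show that contamination is likely.

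A reader might infer that most of the immunogenicity data are unprotected, because 84% of the time to month 6 is. That does not follow: samples through Day 28 are largely covered, and the primary safety endpoint is untouched. Nor does it follow that eligibility must bar planned boosters out to 12 months. That trades recruitment against cleaner late titres, and the analysis rule deals with the bias without it.

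The pre-dosing gap of at most 12 days is a narrower matter. The selection below 20 IU/ml may no longer hold at dosing. Eligibility is checked again at Visit 2 (VI.3.3) and vaccination history updated (VII.1), but a vaccine on Day −35, for example, breaches no criterion. The effect is on eligibility and on reading the colonization results, since III.2 reports higher pre-vaccination antibody (FHA, PRN and fimbriae 2/3) in high-dose subjects who stayed culture-negative. It does not inflate the responder count.

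**What to change.** - **SAP 2.1.3 and 3.1.2:** extend the existing separate-reporting rule to every antibody and cellular sample taken after any non-study pertussis-containing vaccine, at any time up to the last visit. Identify these samples from the vaccine dates in the CRF. Samples taken before the vaccine stay in the main analysis.
- **Sensitivity analysis:** show the mITT result with those samples included. State whether samples set aside count as missing in the SAP 2.1.3 robustness analysis, which imputes the placebo median.
- **Data capture:** the Diary is returned at Visit 8, so the Visit 9 and 10 questions on concomitant medication should ask explicitly about vaccines and their dates.
- **Day 0 serology:** report Day 0 PT and PRN IgG against the 20 IU/ml cut-off, by group.
- **Continuation decision:** reconcile the synopsis with VII.3 on who decides.

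The cost is SAP wording, one extra table, and a few late samples leaving the main immunogenicity table. The allowance for a needed vaccine and the follow-up schedule do not change.
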